6.2. Preparation/Handling/Storage/Accountability

- The study intervention will be packaged and labeled with double blind labels. Each label will be printed with a random and unique container identification (ID) number that is linked to a serialized randomization list.
- An interactive response technology (IRT) system will be used for the randomization of participants into treatment groups and for study intervention assignment.
- The study intervention assignment/dispensing events will be converted to an order for direct shipment of the study intervention to the participant.
- Study intervention shipped at randomization will be sufficient to treat SD lesions through Day 21. Participants will receive one further study intervention supply shipment sufficient to treat SD lesions from Day 22 through Day 43.
- Participants will receive instructions on how to report receipt, store, use and return the study intervention. At each scheduled assessment, tubes can be reviewed by the RTC or CIG.
- A pharmacy service provider will be appointed by the sponsor to support storage and shipment of study intervention, documentation of study intervention assignment, collection and return of study intervention, and completion of study intervention accountability.
- See the investigational product manual for more detailed information.

6.3. Measures to Minimize Bias: Randomization and Blinding

Study using IRT	All participants will be centrally assigned to randomized study intervention using an Interactive Response (IRT) Technology System. Before the study is initiated the log in information & directions for use of the IRT will be provided to the Investigator and appropriately trained designees. Study intervention will be dispensed as summarized in Schedule of Activities .
-----------------	------------------------------------------------------------------------------------------------------------------------------------------------------------------------------------------------------------------------------------------------------------------------------------------------------------------------------------------------------------------------------------------------------

	Returned study intervention should not be re-dispensed to the participants.
Blind Break (IRT)	
The IRT will be programmed with blind-breaking instructions. In case of an emergency, the investigator or sponsor has the sole responsibility for determining if unblinding of a participant's treatment assignment is warranted. Participant safety must always be the first consideration in making such a determination. If the investigator decides that unblinding is warranted, the investigator should make every effort to contact the sponsor prior to unblinding a participant's treatment assignment unless this could delay emergency treatment of the participant. If a participant's treatment assignment is unblinded, the sponsor must be notified within 24 hours after breaking the blind. The date and reason that the blind was broken must be recorded in the source documentation and case report form, as applicable.
 
An IA may be performed during the conduct of the study. Participants or study sites will not be unblinded as a result of a meeting a futility threshold.

6.4. Study Intervention Compliance

- Participant compliance with study intervention will be assessed by Investigator (or designee) review of eDiary responses.
- A participant will be considered compliant with the dosing regimen if they receive 80% to 120% of the expected number of doses, in accordance with the protocol.

6.5. Concomitant Therapy

Any medication (including over-the-counter or prescription medicines, vitamins, and/or herbal supplements), vaccine or non-medication therapies that the participant is receiving at the time of enrollment or receives during the study must be recorded at all study visits/contacts.

All concomitant medications taken during the study must be recorded in study records with indication, reference to any associated adverse event, dose, and start and stop dates of administration.

The Pfizer Medical Monitor should be consulted if there are any questions regarding concomitant or prior therapy for SD prior to determining participant eligibility.

6.5.1. Medications Prohibited Prior to Randomization

Classes of medications and non-medication therapies that may alter the course of SD and for which washout is required prior to randomization are listed below. If a participant requires a

washout, the investigator/designee will provide instructions on discontinuing the prohibited medication(s) or non-medication therapy at the screening visit.

Medications Prohibited 12 weeks or 5 half-lives (whichever is longer) Prior to Randomization

- Biological drugs (e.g., dupilumab, etanercept, ustekinumab, secukinumab, adalimumab, infliximab) used primarily for immunosuppressant or immunomodulation to treat a pre-existing chronic inflammatory disease.

Medications/Therapies Prohibited 28 Days Prior to Randomization

- Use of systemic (oral, parenteral) corticosteroids.

Note: Participants on stable use (regular regimen) of intranasal/inhaled/ophthalmic corticosteroids for at least 14 days of intranasal/inhaled/ophthalmic corticosteroids with ≥ 14 days of consistent use prior to randomization are permitted to continue use of intranasal/inhaled/ophthalmic corticosteroids but must not alter or stop their regimen during the study.

- Use of systemic immunosuppressive agents, including but not limited to methotrexate, cyclosporine, tacrolimus, Janus kinase (JAK) inhibitors (eg tofacitinib), azathioprine, 6 mercaptopurine, cyclophosphamide, chlorambucil, rituximab, antilymphocyte globulin, hydroxychloroquine, or mycophenolate mofetil (MMF).

Medications Prohibited 14 Days Prior to Randomization

- Use of oral or parenteral antibiotics for SD.
- Use of topical corticosteroids (TCS) or topical calcineurin inhibitor (TCI) anywhere on the body.
- Use of topical antihistamines anywhere on the body.

Medications Prohibited 7 Days Prior to Randomization

- Use of topical antibacterial medications or products, including soaps, bleach baths, or topical sodium hypochlorite-based products anywhere on the body
- Escalating, decreasing, or as-needed (PRN) use of topical or systemic antihistamines.

Note: Participants on stable dose of oral antihistamines (sedating or non-sedating) for at least 7 days of consistent use prior to randomization are permitted to continue use of oral antihistamines with minimum alteration of dose/regimen during the study.

Medications Prohibited 1 Day Prior to Randomization

- Use of non-medicated emollients (NOTE: can be used on other regions of body, except on lower extremities).

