1.2. Schema

1.3. Schedule of Activities (SoA)

1.3.1. Screening, Pre-randomization and Randomization

Procedure	Screening Period				Notes
	Screening Visit (Home Visit)	Pre-Randomization Period	Randomization (telemedicine)	Training Visit (Home Visit)	
Day(s)	-28 to -15	-14 to -8	-7 to -2	-2 to +1	
Window (days)	±2	±2	±2	±2	
Enrollment					
Informed consent	X				Section 10.1.3
Demographics, medical history, SD history, SD prior treatments	X				At screening, the participant's primary care physician and subspecialist physician contact information may be collected. Disease history regarding specific comorbid conditions to be recorded on the eCRF. Section 8.2.1 .
Inclusion and exclusion criteria	X	X	X		Investigator reviews all screening period information (eg HVP face to face assessments, HVP scoring, and eDiary) to confirm participant meets all study entry criteria. Section 8
Mini-Mental State Examination-2 (MMSE-2, Brief Version)	X				To be performed by HVP at screening visit. See Section 8.2.6 .
Fitzpatrick Skin Type Assessment	X				To be performed by HVP at screening visit. See Section 8.2.7 .
Randomization by IRT			X		Randomization will result in an order for direct shipment of the study intervention to the participant. See Section 6.3

Procedure	Screening Period				Notes
	Screening Visit (Home Visit)	Pre-Randomization Period	Randomization (telemedicine)	Training Visit (Home Visit)	
Day(s)	-28 to -15	-14 to -8	-7 to -2	-2 to +1	
Window (days)	±2	±2	±2	±2	
Clinical Examination					
Vital Signs	X				To be performed by HVP at home visit. Section 8.2.3
ECG	X				To be performed by HVP at the screening visit. Section 8.2.4
Height and Weight	X				To be performed by HVP at the screening visit. Section 8.2.2
Complete physical examination	X				To be performed by HVP at the screening visit. The participant's family member, friend, or advocate may be present if requested by the participant. Section 8.2.2
Application site (skin) examination	X			X	To be performed by HVP at the screening visit (as part of the complete physical examination) and Training Visit. Section 8.2.2
Laboratory Procedures					
Clinical chemistry, Hemoglobin A1c, PT/INR, and hematology (central lab)	X				To be performed by HVP at the screening visit. Section 8.2.5 , Section 10.2
FSH	X				To confirm postmenopausal status for female participants only. Section 10.4
Efficacy Evaluation					

Procedure	Screening Period				Notes

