Lesional % of Body Surface Area (BSA)	X	X	X	X	X	X	X		X	Completed by HVP at all home visits. Completed by Central Reader for all weekly static digital images. Section 8.1.4.3
Patient Reported Outcomes										

Procedure	Intervention Period (telemedicine) Visits and Week 6/EOT or Early Termination (home) Visit							End of Study (follow-up) (telemedicine)	Unplanned Safety Assessment (home visit or telemedicine visit)	Notes
Day(s)	1	8	15	22	29	36	43	71		Day 1 is the first day of intervention applied. Randomization, Day 8, 15, 22, 29, 36, and Follow-up (Day 71) are scheduled telemedicine contacts. The contact may be conducted solely by phone in the event of technical problems. Interviews may be extended over 2 days to accommodate unforeseen circumstances. Section 8 .
Week(s)	0	1	2	3	4	5	6	At least 28 days after the last dose		End of treatment (home) visit to be performed by HVP at Week 6 (Day 43) or at early termination.
Window (days)		±2	±2	±2	±2	±2	±2	+7		
Serious and non-serious AE reporting	X	X	X	X	X	X	X	X	X	Including AEs reported during referral clinic visits Section 8.3
Study Intervention										
Prior and Concomitant medications / therapies recording on eCRFs	X	X	X	X	X	X	X	X	X	Section 6.5
Study intervention dispensing			X							At Day 15, participants confirmed to be continuing in the study will have a second study intervention supply processed in the IRT system and shipped for use beginning Day 22. Section 6.3
Self-administration of ointment	→	→	→	→	→	→	→			Participants will begin applying study intervention the morning after it is received.

Procedure	Intervention Period (telemedicine) Visits and Week 6/EOT or Early Termination (home) Visit							End of Study (follow-up) (telemedicine)	Unplanned Safety Assessment (home visit or telemedicine visit)	Notes
Day(s)	1	8	15	22	29	36	43	71		Day 1 is the first day of intervention applied. Randomization, Day 8, 15, 22, 29, 36, and Follow-up (Day 71) are scheduled telemedicine contacts. The contact may be conducted solely by phone in the event of technical problems. Interviews may be extended over 2 days to accommodate unforeseen circumstances. Section 8 .
Week(s)	0	1	2	3	4	5	6	At least 28 days after the last dose		End of treatment (home) visit to be performed by HVP at Week 6 (Day 43) or at early termination.
Window (days)		±2	±2	±2	±2	±2	±2	+7		
eDiary completion for:	→	→	→	→	→	→	→			Section 6.5
• study intervention compliance										
• compression therapies										

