4. STUDY DESIGN

4.1. Overall Design

Study C3291038 is a Phase 2a, randomized, double-blind, vehicle-controlled, parallel-group, proof-of-concept study to evaluate the efficacy, safety, and local tolerability of 6 weeks of treatment with crisaborole in adult participants with SD without active skin ulceration. Approximately 70 eligible participants will be randomized into the double-blind treatment period in a 1:1 ratio to receive crisaborole ointment, 2%, or vehicle twice daily for 6 weeks.

The study will recruit male and female participants aged ≥ 45 years with a clinical diagnosis of SD. Participants who meet all inclusion but none of the exclusion criteria presented in [Section 5](#) will be eligible to participate in the study. If a participant meets any of the exclusion criteria, the participant will be excluded.

The total duration of participation in the study will be up to 14 weeks, including up to 4 weeks for screening, a 6-week double-blind treatment period, and a follow-up period of 4 weeks after treatment completion.

Study enrollment and management will be de-centralized, where participants do not visit an investigator or a clinic for clinical assessment. The participants will participate in the study at home. The sponsor (or designee) will provide home visits by qualified home visit practitioners (HVP), remote contact by telemedicine, and clinical database electronic case report forms (eCRFs), eDiary, and other electronic data entries from 3rd party vendors for study data collection.

Participants who withdraw from further study intervention treatment (but do not withdraw consent for further data gathering) should continue to complete all scheduled assessments at the EOT visit and complete the follow-up phase of the study.

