5. Has a history of angioedema or anaphylaxis to topical products or known sensitivity to any of the components of the study interventions.
6. History of or active suicidal ideation or behavior, or chronic psychiatric abnormality that may increase the risk associated with study participation or study intervention administration or may interfere with the interpretation of study results and, in the judgment of the investigator, would make the participant inappropriate for entry into this study.
7. Has a history of cancer or has undergone treatment for any type of cancer within 5 years (except squamous cell carcinoma, basal cell carcinoma, or carcinoma in situ of the skin, curatively treated with cryosurgery or surgical excision only).
8. Has received a solid organ (eg kidney, liver, heart, or lung) transplant.

Prior/Concomitant Therapy

9. Has received any of the prohibited medications/therapies that may alter the course of SD without the required minimum washout period or anticipated concomitant use of any of the prohibited medications/therapy (See [Section 6.5.1](#)).
10. Had previous treatment or is currently being treated with crisaborole, or other topical or systemic PDE-4 inhibitor.
11. Participants on biological drugs (eg dupilumab, etanercept, ustekinumab, secukinumab, adalimumab, infliximab) (See [Section 6.5.1](#)).
12. Has a concurrent medical condition which requires use of systemic immunosuppressive agent(s) (See [Section 6.5.1](#) for prohibited medications).

Other Exclusions

13. Has any planned surgical or medical procedure that would interfere with study participation or influence study results.
14. Women of child-bearing potential (WOCBP) are not eligible for this study (See [Appendix 4](#)).
15. Mini-Mental State Examination-2 (MMSE-2, Brief Version) score of <13 (range 0 to 16).
16. Has any of the following laboratory abnormalities confirmed at screening:
Hemoglobin value <9.0 g/dL; Platelet count <100,000/mm³; INR > 3.5; Hemoglobin A1C ≥10.0%.

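### A 28-day washout begun on instruction at the screening visit does not fit the nominal schedule, which leaves only 8 to 26 days before randomization

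*Protocol*

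**What the plan says.** Protocol Section 6.5.1 groups prohibited drugs by the time they must be absent before randomization. For a participant who needs a washout, "the investigator/designee will provide instructions on discontinuing the prohibited medication(s) or non-medication therapy at the screening visit". The group headed "Medications/Therapies Prohibited 28 Days Prior to Randomization" holds systemic corticosteroids and systemic immunosuppressants. Its note exempts only stable intranasal, inhaled and ophthalmic corticosteroids.

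The Schedule of Activities (Section 1.3.1) puts the screening visit on Day -28 to -15 and randomization on Day -7 to -2, each with a ±2-day window. Section 4.1 describes a study "including up to 4 weeks for screening". On shipment, Section 1.3.1 notes: "Randomization will result in an order for direct shipment of the study intervention to the participant". Section 1.3.2 adds: "Participants will begin applying study intervention the morning after it is received".

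Exclusion 9 (Section 5.2) removes anyone who has had a prohibited drug "without the required minimum washout period". Exclusion 11 bars participants on biologics. Exclusion 12 bars those whose condition requires systemic immunosuppression. Waivers are not allowed (Sections 5 and 8), and screen failures may be rescreened (Section 5.4).

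Section 6.5.3 permits oral corticosteroids up to 15 mg prednisone equivalent daily for chronic non-dermatologic conditions, if stable for at least 2 weeks before screening. Section 6.5.2 prohibits oral corticosteroids from Day 1 to end of treatment and makes no exception for that use.

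**The concern.** Section 6.5.1 starts a trial-directed washout at the screening visit, which is also where informed consent is scheduled. If the time from screening to randomization is shorter than the washout, a participant who follows the instruction stops a systemic drug and is still ineligible on the randomization date. What is at stake is the participant's treatment, and a screen failure or delay that could have been foreseen.

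The gap between Sections 6.5.1 and 6.5.3 adds to this. A site that reads Section 6.5.1 alone could tell someone to stop a low-dose oral corticosteroid, for COPD or rheumatoid arthritis for example, that Section 6.5.3 would have let them keep.

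**Working it through.** **Inputs.** Screening Day -28 to -15, randomization Day -7 to -2, windows ±2 days (Section 1.3.1); washout 28 days before randomization (Section 6.5.1); screening up to 4 weeks (Section 4.1); shipment at randomization and first application the morning after receipt (Sections 1.3.1 and 1.3.2).

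**Day numbering (assumption).** There is no Day 0, so Day -k is k days before Day 1. SAP Section 3.4 supports this: it counts Day -6 to Day 1 as 7 days.

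**The plan's own figure.** Day -28 to Day 1 is 28 days, or 4 weeks, which agrees with Section 4.1.

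**Nominal dates.** Interval = randomization day minus screening day.
- Longest: -2 - (-28) = 26 days; shortfall 28 - 26 = 2 days.
- Shortest: -7 - (-15) = 8 days; shortfall 28 - 8 = 20 days.
- No nominal pair of dates reaches 28 days.

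**Within the 4-week limit.** At least 1 of the 28 days falls between randomization and first application, even with same-day delivery. That leaves at most 28 - 1 = 27 days.

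**With ±2 days at both visits.**
- Calendar limit: 26 + 2 + 2 = 30 days.
- Of 18 screening days × 10 randomization days = 180 pairs, 6 reach 28 days.
- Three of the 6 put randomization on Day 1 itself, which the shipment step rules out.
- The three that remain are: screening Day -30 with randomization Day -1 (29 days), Day -30 with Day -2 (28 days), and Day -29 with Day -1 (28 days).
- Randomization on Day -1 needs same-day delivery, and Day -2 needs delivery no later than the next day. All three need screening before Day -28.
- The practical maximum is therefore 29 days. If Day 0 were counted, it would be 30.

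**Drug stopped before screening.** If last use was k days before screening, 28 - k days remain. The longest nominal interval suffices when k is at least 2, and the shortest when k is at least 20. For example, k = 7 leaves 21 days, which fits with screening on or before Day -23 and randomization on Day -2. Exclusion 2 limits this: a treatment change within 28 days before screening, for a concurrent condition associated with SD such as COPD, already excludes the participant.

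**Other classes.** The 7- and 1-day washouts fit even the shortest nominal interval (8 days). The 14-day washout fits if the dates are chosen for it.

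**The case against.** The strongest reply is that the sentence in Section 6.5.1 is a general lead-in to five time classes and applies only if a washout is needed. It does not promise that every class can be started at screening. The windows belong to the schedule, so 28 days can be reached. Exclusion 12 does for immunosuppressants much of what Exclusion 11 does for biologics. Section 6.5.3 lets many corticosteroid users continue. The investigator's eligibility review and Exclusion 9 should stop anyone being randomized too soon, and rescreening is allowed.

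Most of this stands, and it limits the point. A reader might infer that a 28-day washout is impossible; the windows show that it is only rarely feasible. A reader might extend the point to the 12-week biologic class; Exclusion 11 bars anyone on a biologic, so that class works only as a look-back. Exclusion 12 is narrower, because it removes those whose condition requires an immunosuppressant. A few users whose condition does not require one remain.

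The reply does not remove the mismatch. Section 6.5.1 separates no class from the instruction, and nothing extends screening for a washout. Eligibility review and rescreening act after the drug has been stopped. Rescreening may also have to wait, since Exclusion 2 could count that stop as a recent treatment change. The Medical Monitor consult in Section 6.5 helps only partly, because it concerns therapy for SD.

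**Conclusion.** The point holds as a scheduling inconsistency of limited reach. On nominal dates, a 28-day washout begun at screening falls short by 2 to 20 days. With the windows it succeeds only with early screening and same- or next-day delivery. The 29-day ceiling rests on there being no Day 0 and on at least one day between randomization and first application; the 26-day nominal figure does not depend on the shipment step.

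The affected group is small: mainly users of systemic corticosteroids outside the Section 6.5.3 allowance, and the few immunosuppressant users whom Exclusion 12 leaves in. The documents give no number for either.

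A reader might infer that participants enter with drug still on board and that TSS is biased. The documents do not support that: Exclusion 9 and the eligibility review guard against it, and waivers are not allowed. The consequence is an avoidable drug stop with screen failure or delayed entry. It does not touch the sample size, the significance level or the primary analysis. The change is worth considering because it protects participants at little cost.

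**What to change.** In Section 6.5.1, state that a 28-day-class drug must not be stopped for the trial at the screening visit unless the remaining washout can be completed before the scheduled randomization date. Otherwise the class applies as a look-back criterion.

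Separately, add to both Section 6.5.1 and Section 6.5.2 an exception for the stable oral corticosteroids that Section 6.5.3 permits, so that they are neither washed out nor prohibited on study. Amending Section 6.5.1 alone would leave the on-study ban in Section 6.5.2 in conflict with Section 6.5.3.

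The cost is a few sentences of protocol text. Visits, endpoints and sample size stay as they are. The downside is that a few participants are screened later or not at all.

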6.5.2. Medications/Therapies Prohibited During the Study

Classes of medications and non-medication therapies that may alter the SD disease course are prohibited during the study from Day 1 through to the end-of-treatment.

- Biological drugs (eg, dupilumab, etanercept, ustekinumab, secukinumab, adalimumab, infliximab) used primarily for immunosuppressant or immunomodulation to treat a pre-existing chronic inflammatory disease.
- Use of systemic (oral, parenteral) corticosteroids, unless on stable intranasal/inhaled/ophthalmic regimen (see note in [Section 6.5.1](#)).
- Use of TCS or TCI anywhere on the body.
- Use of systemic immunosuppressive agents, including but not limited to methotrexate, cyclosporine, tacrolimus, JAK inhibitors (eg tofacitinib), azathioprine, 6-mercaptopurine, cyclophosphamide, chlorambucil, rituximab, antilymphocyte globulin hydroxychloroquine, or MMF.
- Use of systemic (sedating or non-sedating) antihistamines, unless on stable regimen (see note in [Section 6.5.1](#)).
- Use of any other PDE-4 inhibitor (topical, oral, or parenteral).
- Use of oral or parenteral antibiotics for treatment of infection of SD lesion(s).

Note: Short courses (≤ 14 days) of systemic antibiotics may be given during the study if clinically necessary for the treatment of new onset infections.

- Use of topical antibacterial medications or products, including soaps, bleach baths, or topical sodium hypochlorite-based products on the lower extremities.
- Use of bland (non-medicated) emollients, moisturizers or sunscreen on SD lesions.
- Participation in another drug or device research study.

